Water, Sanitation, and Hygiene Mobile Health Messages as an Innovative Tool to Facilitate Behavior Change

NCT04816552

January 27, 2020

JHSPH IRB Research Plan for New Data Collection

PI Name: [name]

Study Title: Water, Sanitation, and Hygiene Mobile Health Messages as an Innovative Tool to Facilitate

Behavior Change

IRB No.: IRB00009255

PI Version No. / Date: Version 5 / January 27, 2020

I. Aims of the Study: Describe the aims/objectives of the research and/or the project's research questions or hypotheses.

Aim 1. Develop an evidence and theory based WASH mHealth intervention for households in areas with confirmed cholera patients in Dhaka, Bangladesh through formative research

- a. Conduct formative research through in-depth interviews, focus group discussions, and intervention planning workshops with caregivers and household members of young children, and government officials to identify perceptions of WASH behaviors and to inform the development of intervention materials.
- b. Pilot the WASH mHealth intervention in a subset of households, and revise according to feedback.

Aim 2: Evaluate the effectiveness of the developed WASH mHealth intervention in increasing WASH behaviors and reducing fecal contamination on hands and in stored drinking water by conducting a RCT

- a. Recruit and prospectively follow for 12 months 300 households (1200 participants, 4 per household) with a child under five years of age assigned to one of two study arms (150 households per arm). The first arm will receive the CHoBI7 mHealth program (CHoBI7 mHealth program Arm) and the second arm will serve as a Control Arm and only receive a general message on oral rehydration solution (ORS).
- b. Compare the 2 study arms using structured observation of handwashing with soap at stool and food related events, unannounced spot checks of the presence of soap in the cooking and latrine areas of the household, and fecal coliform counts on caregiver hands and in stored drinking water.
- **II.** Background and Rationale: Explain why this study is being done. Summarize briefly what is already known about the issue and reference previously published research, if relevant.

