Unannounced spot check visits will be conducted at baseline, 1 week, and 1 month (habit formation), and 3, 6, 9, and 12 (habit maintenance) months after enrollment in households to observe: (1) the presence of soap in the latrine and cooking areas of the household (within 10 steps); and (2) measure fecal coliform counts in stored drinking water and on hands.

Clinical Surveillance. Participants will be asked questions about their health (e.g. diarrhea, vomiting), and if they have visited a health provider for care or have taken medication (e.g. antibiotics) at baseline, 1 week, and monthly thereafter for the 12 month study period. Participants will also be asked about their intervention exposure (e.g. visits and mobile messages received). Child height and weight will be measured at baseline, and 6 and 12 months.

Power Calculation and Statistical Analysis. Our sample size of 300 households is based on the largest number of households we could recruit based our budget. Our power calculation is summarized in Table 2 below. We will compare demographic and socioeconomic factors between arms to determine whether randomization was successful in defining similar groups of households. We will conduct linear regression models for continuous variables and logistic regression models for binary outcomes to compare intervention arms at specific follow-up times. The predictors in these models will be study arm. Generalized estimating equations will be used for individual level variables to account for clustering in the household, as well as comparing the rate of change over time within households. To investigate potential psychosocial factors mediating the intervention effect, mediation models will be performed using the "INDIRECT" macro. [2, 5] All analyses will be performed using SAS 9.3.

Table 2. Power calculation. Detectable differences for outcomes between intervention and comparison arm for 80% power, assuming 10% loss to follow-up among 300 enrolled households resulting in 270 households at the 12 month follow-up

Outcomes	N	Anticipated % in Control Arm (Based on Current Trial)	Detectable Difference Between Intervention and Control Arms
% Individuals handwashing with soap at a stool or food related event during structured observation (100 randomly selected households per timepoint (400 participants at each visit with 10% loss to follow-up))*	360	25%	16%
% Households with soap present in cooking area at a spot check	270	31%	17%

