% Households with soap present in latrine area at a spot check	270	51%	17%
% Household with stored drinking water <1 CFU/100 MI E.coli (100 randomly selected households per timepoint)	90	8%	23%
% of Hand rinses samples with detectable fecal coliforms (100 randomly selected households per timepoint with 10% loss to follow-up)	90	90%*	24%

^{*}Assuming an intra-class correlation of 0.1 for handwashing with soap of individuals in the same household, for a design effect of 1.3.

- B. Provide a sample size and a justification as to how you arrived at that number. If you use screening procedures to arrive at a final sample a table may be helpful.
- In-Depth Interviews (30-40 Participants): We will conduct in-depth interviews with key audience segments to identify appropriate mHealth messages, including households living in areas identified to have cholera patients, health facility staff and directors, and government officials.
- Focus Group Discussions (60-80 Participants, 6-12 participants per group): We will conduct focus group discussions with the same segments of key stakeholders as the in-depth interviews to identify appropriate WASH intervention messages.
- Intervention Planning Workshops (45-60 participants): These workshops will be held with government officials and health providers to review mHealth messages, and to discussion integration of these messages into the national program for cholera outbreaks.
- Pilot Study (300 Participants (75 households, approximately 4 participants/household)): We will recruit 300 participants (~75 households) for a pilot study of developed mHealth messages. We will follow these households prospectively for up to three months to observe the uptake of the promoted behaviors. Modifications of intervention and study tools will be made according to feedback from pilot study participants.

Randomized Controlled Trial (1200 Participants (300 households, approximately 4

participants/household)): We will recruit 1200 participants (300 households) for a randomized controlled trial of the developed mHealth messages. We will follow these households prospectively for up to twelve months to observe the uptake of the promoted behaviors.

IV. Participants:

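### The baseline comparison cannot show that randomization succeeded, and the arm-only models leave those same baseline data unused where about 45 households per arm are analysed

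*Combined protocol and SAP*

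**What the plan says.** All the relevant text is in the combined protocol and SAP.

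- **Baseline comparison** (Section III.A, Power Calculation and Statistical Analysis): "We will compare demographic and socioeconomic factors between arms to determine whether randomization was successful in defining similar groups of households". The plan does not name the factors, the set of households, a criterion, or what follows if the arms differ.
- **Models** (same paragraph): linear or logistic regression at specific follow-up times, with "The predictors in these models will be study arm". Generalized estimating equations (GEE) are added for clustering within households and for change over time. No covariate is named for them.
- **Randomized set** (Section I, Aim 2a): 300 households, "assigned to one of two study arms (150 households per arm".
- **Analysed sets** (Table 2): handwashing rests on "100 randomly selected households per timepoint (400 participants at each visit with 10% loss to follow-up", with N = 360 people. Stored water also rests on "100 randomly selected households per timepoint", with N = 90. The hand rinse row reads "of Hand rinses samples with detectable fecal coliforms (100 randomly selected households per timepoint with 10% loss to follow-up", again with N = 90. The two soap-presence rows, such as "Households with soap present in cooking area at a spot check", use all 270 retained households.

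The subsets appear only in Table 2. The plan does not say whether the draw is stratified by arm, or whether the same households are kept from visit to visit.

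**The concern.** There are two linked problems. First, the baseline comparison is asked a question it cannot answer. If allocation was done properly, every difference in demographic or socioeconomic factors arose by chance. Similar arms do not prove that the allocation was sound, and dissimilar arms do not prove that it failed.

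Second, the factors are collected and compared but then left out of the models. Adjustment would matter most for handwashing and the two coliform measures, which belong to the primary outcomes and are measured in roughly a third of the households. A reassuring statement about the 300 households could stand beside visit-specific results from groups that differ noticeably. For these measures, a household drawn at follow-up may also lack a baseline outcome value, whereas a socioeconomic measure can be available for every enrolled household.

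**Working it through.** **1. Reproduce Table 2.** The caption sets "Detectable differences for outcomes between intervention and comparison arm for 80% power, assuming 10% loss to follow-up among 300 enrolled households". I used a two-sided 5% test (not stated in the plan, but it reproduces the table), pooled variance, equal arms and no continuity correction. Handwashing uses 180/1.3 = 138.5 effective people per arm, soap 135 households per arm, and water and hand rinses 45 per arm.

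| Row | Stated | Recomputed |
|---|---|---|
| Handwashing | 16 | 15.75 |
| Soap, cooking area | 17 | 16.6 |
| Soap, latrine area | 17 | 16.7 |
| Stored water | 23 | 23.1 |
| Hand rinse | 24 | 24.2 |

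The table reproduces, and its fit supports 45 per arm. For handwashing, 360 people at 4 per household is also 90 households, or 45 per arm.

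**2. Balance in the 300 against balance in the subset.** Suppose 75 of 150 households in each arm have a yes/no factor, so the 300 are exactly balanced. Draw 45 of 150 per arm without replacement.

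- SD of the arm difference = sqrt(2 × 0.25/45 × 105/149) = 0.088, or 8.8 points.
- From the exact hypergeometric distribution, a gap of at least 10 points (5 or more households) occurs in 25.8% of draws. A gap of at least 15 points (7 or more households) occurs in 10.2%.
- At 40% and 30% prevalence, the 15-point figure is 9.5% and 7.4%.

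In a simulation of 20,000 trials, the imbalance in the full set and in the subset correlated only 0.55.

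**3. Overall validity.** The same simulation used a covariate that explained 25% of the outcome variance. The arm-only test in a random 45 per arm rejected a true null in 5.1% of trials.

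**4. Shift in the handwashing estimate, given an imbalance.** Inputs from Table 2: 25% in the control arm, intra-class correlation 0.1, design effect 1.3.

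- Individual variance: 0.25 × 0.75 = 0.1875. Between-household part: 0.1 × 0.1875 = 0.01875.
- Variance of a household mean of 4 people: 0.1875 × 1.3/4 = 0.0609. SE of the arm difference: sqrt(2 × 0.0609/45) = 0.0520.
- Assume that the factor has 50% prevalence and explains a share R² of between-household variance, with R² from 0.1 to 0.3. Its effect b satisfies b² × 0.25 = R² × 0.01875, so b = 0.087 to 0.15.
- Shift at a 15-point imbalance: 0.15 × b = 1.3 to 2.25 points.
- Given the imbalance, the factor no longer adds sampling variance. The SD falls to sqrt(2 × (0.0609 − R² × 0.01875)/45) = 0.0512 to 0.0496, while the test still uses 0.0520.
- Conditional rejection under no effect, P(|estimate| > 1.96 × 0.0520): **5.4% to 6.0%**. With exact balance it is below 5% (about 4.0% at R² = 0.3), which is why the overall rate stays at 5%.

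**5. Precision gained by adjusting (handwashing).** Between-household share of the household-mean variance: 0.01875/0.0609 = 0.31. Detectable difference: 15.75 × sqrt(1 − 0.31 × R²) = **15.5, 15.3 and 15.0** for R² = 0.1, 0.2 and 0.3.

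**6. Rough guide for hand rinses.** If a covariate explained 10-30% of total outcome variance (a stronger assumption than in step 5, with a linear approximation), the factor sqrt(1 − R²) would take 24.2 points to about 23 to 20.

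**The case against.** The strongest reply is that arm-only analysis is a legitimate primary analysis. Randomization acts on the 300 households, so that is the right set in which to examine the allocation. A random subset of randomized households is still a randomized comparison, and the standard error already allows for chance imbalance. All of this stands. It rules out several stronger readings that a reader might infer:

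- **That the check is made in the wrong set.** It is not. It only fails to describe the groups analysed for three of the five Table 2 rows. That it covers all enrolled households is itself the natural reading, not something the plan states.
- **That the arm-only tests are biased or have inflated error.** They are not; see step 3.
- **That a 15-point imbalance in a factor worth 20 handwashing points raises the false-positive risk to 8.9%.** That figure adds the 3-point shift to the full standard error of 0.052, which already contains the factor's variance. Removing that part gives 6.8%. Such a factor would also explain 0.01/0.01875 = 53% of between-household variance, well above the 10-30% used here.
- **That a large imbalance at some visit is close to even odds.** Six independent follow-up draws would give 1 − (1 − 0.102)^6 = 47% for at least one gap of 15 points or more. The plan does not say that households are redrawn. One fixed panel gives 10%, with the imbalance present at every visit.
- **That the check would often declare a sound randomization failed.** Ten independent tests at 5% would flag at least one difference 40% of the time, but the plan states no test, threshold or number of factors.

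The reply does not rescue the stated purpose of the comparison, and it does not explain why the baseline data are left out of the models.

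**Conclusion.** The concern holds in a modest form. The comparison is given a purpose it cannot serve, and the arm-only models pass over baseline data that would help. No Table 2 figure is wrong on this point, no planned test becomes invalid, and the two soap-presence outcomes are untouched by the subset argument.

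For handwashing, the cost of leaving the models as they are is up to about 0.75 points of detectable difference. When a 15-point imbalance does occur, the estimate also shifts by roughly 1 to 2 points. These sizes rest on the assumed 10-30% share of between-household variance, a 50% factor, and an even split of 45 per arm. If the draw is not stratified by arm, one arm's share of the 90 could range from 37 to 53 (95% range). The change is worth making because it is almost free and because naming the covariate now prevents a choice made after imbalances are seen.

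**What to change.** Replace the comparison sentence with: *Baseline demographic and socioeconomic factors will be summarised by arm, without a verdict on randomization, for all randomized households and for the households analysed at each timepoint.*

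Change the model sentence so that the handwashing and coliform models contain study arm and one pre-named baseline household socioeconomic measure, collected in all households and included whatever the summary shows. Report the arm effect as a standardised difference on each outcome's planned scale, since adding a covariate to a logistic model changes what its odds ratio means. Give the arm-only result as a sensitivity analysis. It would also help to state whether the 100 households are drawn within arm and whether the same households are kept across visits.

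The cost is a few sentences and a few lines of code. No new data are needed if a suitable measure is already among the planned socioeconomic factors. The small downside is one extra model term with about 90 households per visit, which is why a single covariate is proposed.

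### Soap-presence outcomes: the visit-specific models use study arm alone and leave out the baseline value already scheduled, giving up precision if baseline predicts follow-up

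*Combined protocol and SAP*

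**What the plan says.** All of the relevant text is in section III.A.

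- **Outcome.** Soap in the cooking and latrine areas, seen at spot checks, is the third of the listed primary outcomes.
- **Schedule.** "Unannounced spot check visits will be conducted at baseline, 1 week, and 1 month (habit formation"), and then at 3, 6, 9 and 12 months. Each spot check records soap in both areas.
- **Model.** Binary outcomes are analysed by "logistic regression models for binary outcomes to compare intervention arms at specific follow-up times". The next sentence reads "The predictors in these models will be study arm". No covariate is named.
- **GEE.** "Generalized estimating equations will be used for individual level variables to account for clustering in the household", and also to compare rates of change within households.
- **Table 2.** The rows "Households with soap present in cooking area at a spot check" and "Households with soap present in latrine area at a spot check" have N = 270, control percentages of 31% and 51%, and a detectable difference of 17 points each. The other rows rest on a subsample, for example "100 randomly selected households per timepoint with 10% loss to follow-up" for hand rinses.

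**The concern.** Soap presence is measured before the intervention in the same households that are analysed later. If a household with soap at baseline tends to have it at follow-up, part of the outcome variation can be explained, and a model with arm alone leaves it in the error.

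The GEE sentence does not fill the gap. Soap presence is a household-level variable, the rate-of-change analysis is separate from the visit-specific comparison that Table 2 powers, and no baseline term is named.

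Only precision is at stake. It matters somewhat more here than usual because "Our sample size of 300 households is based on the largest number of households we could recruit based our budget", so recruiting more households is not an available way to gain it.

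**Working it through.** **Inputs from the documents.** 300 households, 150 per arm; 10% loss, so 270 analysed, or 135 per arm; target power 80%; cooking area 31% vs 48%; latrine area 51% vs 68%.

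**Assumed.** Two-sided 5% test (no alpha is stated); baseline prevalence equal to the control percentage in both arms; baseline-to-follow-up correlation as a range, since none is given.

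**Step 1: reproduce Table 2.** Power = Φ[(d − 1.96·SE0)/SE1], with SE0 = √(2·p̄(1−p̄)/n) and SE1 = √((p0(1−p0)+p1(1−p1))/n).

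- Cooking: p̄ = 0.395, SE0 = 0.0595, SE1 = 0.0586; power = Φ[(0.17 − 0.1166)/0.0586] = 0.819.
- Latrine: p̄ = 0.595, SE0 = 0.0597, SE1 = 0.0588; power = 0.816.

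Solving for 80% power gives detectable differences of 16.6 and 16.7 points, which round to the stated 17.

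**Step 2: add the baseline value.** Simulation with 135 per arm, bivariate-normal latent baseline and follow-up values, logistic Wald test, and 20,000 runs per setting (Monte Carlo SE about 0.003). Unadjusted power was 0.824-0.827 (cooking) and 0.821-0.824 (latrine). The variance ratio is adjusted over unadjusted variance of the risk difference. Equivalent extra households = 270/ratio − 270.

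| Latent correlation, control / intervention | Cooking: ratio, power | Latrine: ratio, power | Extra households |
|---|---|---|---|
| 0.3 / 0.3 | 0.969, 0.834 | 0.966, 0.830 | 9-10 |
| 0.5 / 0.5 | 0.897, 0.859 | 0.895, 0.853 | 31-32 |
| 0.7 / 0.7 | 0.778, 0.903 | 0.772, 0.903 | 77-80 |
| 0.3 / 0.1 | 0.989, 0.824 | 0.985, 0.824 | 3-4 |
| 0.5 / 0.2 | 0.956, 0.839 | 0.952, 0.835 | 12-14 |
| 0.7 / 0.3 | 0.899, 0.861 | 0.885, 0.862 | 30-35 |

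The test on the standardised risk difference itself (robust SE, equal correlation) gives 0.840 / 0.864 / 0.909 for cooking and 0.836 / 0.859 / 0.908 for latrine, against 0.826-0.829 unadjusted.

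**Step 3: closed-form check.** Ratio ≈ 1 − (cC + cT)²/[2·vB·(vC + vT)], where c is the baseline-follow-up covariance in an arm and v a binary variance. For cooking at latent 0.5, the observed correlation is about 0.32 in each arm, so cC ≈ 0.068 and cT ≈ 0.073. With vB = vC = 0.214 and vT = 0.250, the ratio is 1 − 0.0201/0.198 = 0.899. For 0.3 / 0.5 / 0.7 in both arms the formula gives 0.966 / 0.899 / 0.778 (cooking) and 0.964 / 0.894 / 0.771 (latrine), in line with the simulation.

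**Step 4: scale of the correlation.** Latent 0.3 / 0.5 / 0.7 correspond to observed yes/no correlations of about 0.18-0.19 / 0.32-0.33 / 0.46-0.49. A team tabulating earlier data would see the observed scale. There the variance falls by about ρ²: 4% at 0.2, 9% at 0.3, 25% at 0.5. Cooking-area power is then 83.4%, 85.3% and 91.3%. At ρ = 0 a separate simulation gave a ratio of 1.01, which is no material loss.

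**Step 5: validity.** The mean risk difference is 0.170-0.171 with and without adjustment. Under no effect, adjusted type I error is 0.047-0.051 (Wald) and 0.051-0.054 (standardised risk difference). The SE of the log odds ratio rises with adjustment (0.255 to 0.271 at observed 0.3, cooking) although power also rises, because the conditional odds ratio is a different quantity. The effect measure must therefore be named.

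**Step 6: why only soap.** The other outcomes use 100 of 300 households per timepoint. If households are redrawn, about one third have their own baseline. Complete-case adjustment would cut power from 0.81 to 0.37 for handwashing (180/1.3 per arm), and from 0.80 to 0.35 for stored water and for hand rinses (45 per arm each).

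**The case against.** The strongest reply is that nothing is broken. An unadjusted analysis of a randomised trial is accepted practice, it matches Table 2, and the soap outcomes already exceed 80% power. The thin outcomes are stored water and hand rinses (N = 90), which this change does not help. The size rests wholly on an assumed correlation. The top of the range needs latent 0.7 in both arms, between single yes/no checks up to 12 months apart, in a trial meant to change this very behaviour. Weaker tracking in the intervention arm is at least as plausible. There the gain is 0 to 4 points of power, or confidence intervals about 1-6% narrower (1 − √ratio). The rate-of-change analysis may also draw on the baseline data.

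Most of this stands, and it sets the grade: the gain is optional, uncertain and possibly nil. It does not remove the point. The visit-specific models still omit a measured baseline, and adjusting for it costs almost nothing when it predicts poorly. Fixing the choice in advance also prevents a later, data-driven choice between adjusted and unadjusted results.

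**Conclusion.** The point holds as a modest improvement that could be made. The arm-only comparison is valid and has the power that Table 2 claims. Adding baseline soap presence would raise power at 17 points from 0.82-0.83 to somewhere between no change and about 0.90. In households, that is worth between 3 and 80 extra analysed households over the settings tried, and nothing if baseline does not predict follow-up. These figures assume a two-sided 5% test, a latent-normal model, baseline prevalence equal to the control percentage, and a correlation that the documents do not supply. Confidence in the size is therefore medium; the reading of the text is not in doubt.

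**What to change.** Replace the predictor sentence in the statistical analysis paragraph of section III.A with:

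> For soap presence in the cooking and latrine areas, the predictors will be study arm and the household's baseline value of the same outcome (with a category for a missing baseline). The arm effect will be reported as a standardised risk difference, with the arm-only model as a sensitivity analysis. For all other outcomes the predictor will be study arm.

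This keeps the effect on Table 2's scale and keeps every household in the analysis. Do not add a complete-case baseline covariate for handwashing, stored water or hand rinses.

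A repeated-measures model for log10 coliform counts, with baseline as its first visit and no arm difference there, is a separate option and would need an exception in the last sentence above. If households are redrawn, its gain is small: at r = 0.3-0.6, r²/3 = 3-12% lower variance with equal weighting, or 1 − 45/(15/(1−r²)+30) = 3.2-15.8% with optimal weighting.

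The cost is one sentence and a little extra analysis work for the standardised risk difference and the sensitivity analysis. No new data are needed.

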- Randomized Controlled Trial participants must have: (1) at least one household member reporting ownership of an active mobile phone in their possession on the day of enrollment; (2) must also have a child under 5 years of age in their household; (3) must live in an area identified to have cholera patients by the icddr,b surveillance system; and (4) must plan to reside in their household for the next 12 months

• Exclusion Criteria:

Children in foster care will be excluded from all research study activities. If the interviewer becomes aware when talking to an adult respondent (18 years or older) that they appear to have a cognitive limitation, an adult household member may sign the Consent form on their behalf.

No one will be excluded because of age, sex, religion, or sexual preference.

Children younger than 12 years of age will be excluded from the in-depth interviews, focus group discussions, and workshops. Children younger than 12 years of age will not complete the psychosocial factors.

NOTE: If you are recruiting participants or receiving, accessing, or using data from a U.S. health care provider, HIPAA review is likely to be required. If you plan to bring identifiable health information from a foreign country to a U.S. covered entity (e.g., lab at the Hopkins SOM), HIPAA may be triggered. Check "yes" to the HIPAA question in the PHIRST application.

V. Study Procedures:

In this section, provide details of your procedures, particularly as they relate to human subjects. If this is a multi-center study, make the role of JHSPH clear. If the JHSPH will serve as **data coordinating center**, indicate in the sections below which procedures JHSPH will not be performing. Additional information regarding data coordinating centers is requested in a later section. If your study will develop in phases, address each item below by phase.

A. Recruitment Process:

1. Describe how you will identify, approach, and inform potential participants about your study. Include details about who will perform these activities and what their qualifications are.

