Participants in the in-depth interviews, focus groups discussions, intervention planning workshops, and pilot will be recruited by trained research assistants from icddr,b through a combination of purposive and convenience sampling strategies. Individuals participating in an in-depth interview may also be invited to participate in a focus group discussion. Government officials and health facility staff and directors will be contacted by phone or approached at their office. Pilot participants will be selected across the geographic catchment area of Dhaka, Bangladesh based on the neighborhoods (wards) where cholera patients are identified. Randomized controlled trial participants will be randomly selected across the geographic catchment area of Dhaka, Bangladesh based on the neighborhoods (wards) where cholera patients are identified. All potential participants will be read a recruitment script, given an opportunity to ask questions, and then screened and consented to participate by trained icddr,b research assistants. Adults in study households will be recruited before children.

2. Address any privacy issues associated with recruitment. If recruitment itself may put potential participants at risk (if study topic is sensitive, or study population may be stigmatized), explain how you will minimize these risks.

We do not anticipate any privacy issues during recruitment.

B. Consent Process:

- 1. Describe the following details about obtaining informed consent from study participants. If a screening process precedes study enrollment, also describe the consent for screening.
 - A. Who will obtain informed consent, and their qualifications:

In-depth interviews, focus group discussions, and intervention planning workshops: A trained icddr,b research assistant who will be conducting the in-depth interviews, focus group discussions, and intervention planning workshops will obtain informed consent from adult participants and assent from children (12-17 years), and informed consent (parental permission) from a parent or guardian.

Pilot trials: A trained icddr,b research assistant will obtain informed consent from adult participants and assent from children (12-17 years), and informed consent from a parent or guardian for our pilot study.

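### Trial households are sampled by ward, but no balancing of arms by area is described and the models contain study arm only, so a modest amount of precision is lost if wards differ

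*Combined protocol and SAP*

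**What the plan says.** - **Sampling.** Section V.A.1 (Recruitment Process) says that trial households will be "randomly selected across the geographic catchment area of Dhaka, Bangladesh based on the neighborhoods (wards) where cholera patients are identified". The eligibility criteria in section IV add that they "must live in an area identified to have cholera patients by the icddr,b surveillance system". Location is therefore known before a household is allocated.
- **Allocation.** Aim 2a says that households are "assigned to one of two study arms (150 households per arm"). It does not describe sequence generation, blocks or strata, and neither does any other section.
- **Balance.** The one step on balance comes after the fact, in section III.A (Power Calculation and Statistical Analysis): "We will compare demographic and socioeconomic factors between arms to determine whether randomization was successful". Ward is not named there.
- **Analysis.** The same section plans linear and logistic regression at specific follow-up times and says "The predictors in these models will be study arm". For clustering it says "Generalized estimating equations will be used for individual level variables to account for clustering in the household". Ward is neither a covariate nor a level of correlation.
- **Subsamples.** In Table 2 the handwashing, stored-water and hand-rinse rows rest on 100 randomly chosen households per timepoint. The plan does not say that these are drawn by area or by arm.
- **Size.** The 300 households are the most that the budget allows.

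**The concern.** When arms are compared without regard to area, any real difference between areas counts as noise and can fall unevenly between the arms by chance. Balancing the arms within areas and then including area in the model removes that part of the variance. It needs no extra households, which matters because the number is capped by budget and Table 2 is set at 80% power with little to spare. There is also a question of consistency. If the team does block by area in practice but fits the arm-only model, the test no longer matches the design and rejects too rarely.

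**Working it through.** **Inputs from the documents (Table 2 and its footnote).** 80% power; 300 households less 10% gives 270, or 135 per arm; control rates and detectable differences as in the table below; household ICC 0.1 with design effect 1.3 for handwashing.

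**Assumptions.** Two-sided alpha of 0.05 (not stated in the documents). Ward ICC 0.02 to 0.10 (not stated). The number of wards and the households per ward are not stated either.

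**Step 1: reproduce Table 2.** With n per arm, p̄ the mean of the two rates and Δ their difference:

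power = Φ{ [Δ − 1.96·√(2p̄(1−p̄)/n)] / √([p₁(1−p₁)+p₂(1−p₂)]/n) }

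Soap in the cooking area: n = 135, 31% vs 48%, p̄ = 0.395. The standard errors are 0.0595 (null) and 0.0586 (alternative). (0.17 − 1.96 × 0.0595)/0.0586 = 0.91, so power is 81.9%. For handwashing, n = 360/2/1.3 = 138.5. All five rows come out within 2 points of 80%, without a continuity correction.

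**Step 2: approximate gain from using area.** If arms are balanced within areas and area is in the analysis, the between-area share ρ of the variance drops out, so effective N = N/(1 − ρ). For N = 270: 270/0.95 = 284 and 270/0.90 = 300.

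| Outcome | n per arm | Control | Stated difference | Computed difference | Power as planned | ρ = 0.02 | ρ = 0.05 | ρ = 0.10 |
|---|---|---|---|---|---|---|---|---|
| Handwashing | 138.5 | 25% | 16% | 15.8% | 81.2% | 81.9% | 83.1% | 85.1% |
| Soap, cooking area | 135 | 31% | 17% | 16.6% | 81.9% | 82.7% | 83.8% | 85.7% |
| Soap, latrine area | 135 | 51% | 17% | 16.7% | 81.6% | 82.3% | 83.5% | 85.4% |
| Stored water | 45 | 8% | 23% | 23.1% | 79.7% | 80.5% | 81.7% | 83.8% |
| Hand rinse | 45 | 90% | 24% | 24.2% | 79.5% | 80.3% | 81.5% | 83.6% |

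For the cooking-area row the detectable difference moves from 16.6% to 16.2% (ρ = 0.05) or 15.7% (ρ = 0.10). The formula takes no account of the price of having many strata, so simulation is needed.

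**Step 3: simulation, cooking area, N = 270.** Simple allocation with an arm-only test was set against blocked allocation with an area-stratified Mantel-Haenszel test. Monte Carlo error is about 1 point in the 48% runs and up to 0.7 in the 47.6% runs.
- 10 areas, 31% vs 48%: 82.9% to 83.7% (ICC 0.05) and 82.3% to 86.8% (0.10).
- 10 areas, 31% vs 47.6%: 81.4% to 82.6% (0.05) and 80.8% to 83.7% (0.10).
- 90 areas of 3 households, 31% vs 48%: 82.9% to 80.5% (0.05) and 81.7% to 80.9% (0.10). Here the gain has reversed.

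With 10 areas the gain is about 1 to 5 points at ICC 0.05 to 0.10.

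**Step 4: simulation, subsampled outcomes, 90 of 300 households analysed.** Simple allocation with the arm-only test gives about 80-82% on both the water and the hand-rinse rows.
- 30 zones of 10, subsample drawn without regard to zone: 90/30 = 3 analysed households per zone on average. Many zones then have only one arm or only one outcome and contribute nothing. Power falls to 68-76% at ICC 0.02 to 0.10, a loss of about 5 to 13 points.
- 10 zones of 30, subsample drawn without regard to zone: at ICC 0.02 to 0.05, water falls from 81-82% to 79-80%, and hand rinse is flat or slightly lower.
- 10 zones of 30, subsample drawn within zone and arm: no change at ICC 0.02, and a gain of about 1 to 4 points at 0.05 to 0.10.

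**Step 5: validity.** With simple allocation the arm-only test rejected a true null in 4.0-6.6% of runs, which is near 5%. With blocked allocation and area left out of the test, rejection fell to 3.5-4.4% at ICC 0.05 to 0.10 with 10 or 30 areas.

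**The case against.** The planned analysis is sound as it stands. Comparing randomised households without covariates is valid, its type I error is near 5%, and Table 2 holds. The size of any gain rests on a ward ICC that the documents do not give, and at 0.02 it is close to nothing. The plan's silence on allocation is not a decision against blocking, since no allocation method of any kind is described. Nor is area the only route to precision: the outcomes are also measured at baseline, and the GEE is meant to compare change within households. Most seriously, the obvious remedy of one stratum per ward, or per small group of wards, would do harm. Three of the five Table 2 rows rest on about 90 analysed households, and thin strata lose more on the water and hand-rinse rows than the soap rows gain.

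All of this stands, and it limits the point. It does not remove it. Area is known beforehand, the model sentence leaves it out, and with few, large zones and matched subsampling the simulations show no loss at ICC 0.02 and a small gain above that.

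**Conclusion.** The point holds as a modest loss of efficiency. Over an assumed ICC of 0.02 to 0.10, using area in allocation and analysis together is worth about 0 to 5 power points, near zero at the lower end. This assumes about 10 large zones, subsamples drawn within zone and arm, and zones that themselves carry the assumed ICC. Merging unlike wards into one zone would shrink the gain. The handwashing row was assessed by the approximation only.

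Three stronger readings are tempting, and the documents do not support them.
- A reader might infer that the arm-only comparison is biased or that Table 2 is wrong. Neither follows: the comparison is of randomised households, and the table reproduces.
- A reader might infer that allocation is known to be unblocked. The documents say nothing either way.
- A reader might expect a large gain. At ICC 0.20 simulated cooking-area power reaches about 88%, but 0.20 is twice the only ICC in the documents, which is 0.1 for handwashing by members of one household. Nothing supports so high a value between wards.

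**What to change.** 1. Before allocation, group the wards into about 10 or fewer zones of roughly 30 or more households each, and randomise in permuted blocks within zone.
2. Draw the 100-household subsample at each timepoint within zone and arm.
3. In section III.A, change the model sentence so that the predictors are study arm and randomisation zone, and carry the same term into the GEE. Steps 1 to 3 belong together.
4. Do not use zones of 8 to 10 households, or single small wards, as strata.
5. If allocation has already been done, report the method used and include in the models any area strata that were blocked on. If none were, the arm-only comparison remains valid.

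The cost is one allocation list, a rule for drawing the subsamples and one model term, with no extra households, visits or samples. The zones must be fixed in advance, and the gain is near zero if wards hardly differ. In the logistic models the adjusted odds ratio is conditional on zone, a different quantity from the unadjusted one, and its standard error need not shrink. Precision should therefore be judged on the risk-difference scale.
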